4. VERSION DATE 7/26/16

5. SPECIFIC AIMS

Aim 1: Assess the relationship of treatment with the combination of dronabinol and clonidine or placebo on cannabis use patterns in cannabis-dependent subjects with an Axis 1 psychiatric disorder.

Aim 2: Assess the relationship of treatment with the combination of dronabinol and clonidine or placebo on cannabis withdrawal symptoms in cannabis-dependent subjects with an Axis 1 psychiatric disorder.

6. BACKGROUND AND SIGNIFICANCE

People with schizophrenia are more likely than healthy people to abuse cannabis (Kovasznay et al. 1997). Although it is unclear why this is true, patients with schizophrenia may use cannabis to alleviate unpleasant affective symptoms (Gregg et al. 2007). Cannabis dependence may trigger psychotic symptoms and worsen the outcome of the disease in this group (Linszen et al. 1994). Unfortunately, effective medications for cannabis-dependent schizophrenic individuals have not been identified.

Combinations of medications may offer advantages not available with monotherapy. Haney et al. (2008) showed that the combination of THC and the α_2 -adrenergic receptor agonist lofexidine decreased symptoms of cannabis withdrawal, craving, and relapse in a human lab study of daily cannabis smokers. Although lofexidine is not approved for use by the United States Food and Drug Administration (FDA), clonidine, another α_2 - adrenergic receptor agonist, is FDA-approved and commonly used in clinical practice. Therefore, we build upon this exciting finding by proposing a pilot study of the combination of THC, specifically Dronabinol (Marinol®, Solvay Pharmaceuticals, Marietta, GA, or generic, specific manufacturer to be determined) which is an orally-active cannabinoid agonist that is approved by the FDA for the treatment of anorexia associated with weight loss in patients with AIDS and nausea and vomiting associated with cancer chemotherapy (Marinol® product information); and clonidine as a treatment for cannabis dependence in schizophrenic individuals.

Our study may provide initial evidence for a readily available, effective treatment for cannabis dependence in subjects with schizophrenia. This combination treatment may reduce cannabis withdrawal symptoms that function as an obstacle for subjects with schizophrenia trying to stop using cannabis.

Version Date: July 26, 2016

7. RESEARCH DESIGN AND METHODS

Briefly describe study design and anticipated enrollment, i.e., number of subjects to be enrolled by researchers study-wide and by McLean researchers. Provide a brief summary of the eligibility criteria (for example, age range, gender, medical condition). Include any local site restrictions, for example, "Enrollment at McLean will be limited to adults although the sponsor's protocol is open to both children and adults."

8.1. Overview

We will conduct a Stage 1 pilot feasibility study at McLean Hospital to develop a combination of medication protocol to treat cannabis dependence in subjects with schizophrenia, schizoaffective, or any Axis I disorder. In a randomized, double-blind, placebo-controlled trial, 18 cannabis-dependent male an female subjects ages 18-45 with an Axis 1 psychiatric disorder will receive medical management (MM) over a 10-week period, with half receiving treatment with the combination of dronabinol and clonidine and half receiving placebo. Subjects will receive either the combination of dronabinol 5 mg by mouth three times daily and clonidine 0.1 mg my mouth twice daily or placebo in addition to MM over a 10-week treatment period. A follow-up visit after treatment at week 14 will evaluate the durability of treatment effects on drug use and psychosocial outcomes. Primary outcomes will include self-report of cannabis smoking and results of quantitative urine drug screens for cannabis. We also will assess cannabis withdrawal symptoms, including mood and craving. Mixed models ANOVA will be used to analyze the data.

8.2. Participants

Subjects are cannabis-dependent male and female volunteers with mental illness ages 18-45 years old and will be recruited via newspaper advertisements, word of mouth, web-based advertisements, and the Psychotic Division Clinical Research Core (Protocol # 2009-P-002016)..

A total of 18 cannabis-dependent volunteers with (9 men, 9 women) an Axis 1 psychiatric Disorder will serve as subjects. Factoring in a potential 20% dropout of those who actually begin the protocol, we estimate that 7-8 people will probably be exposed to dronabinol in this pilot study. In order to meet the target sample of 18 completers (8 subjects per group), we expect to recruit about 50 subjects and have 35 sign the informed consent form. Of those who sign the informed consent form, 14-18 will probably end up being randomized.

Women must use a medically-approved method of contraception to participate in the study (e.g. birth control pills, IUD, condoms). During the physical, the physician will ensure that the potential volunteer is using adequate methods to prevent pregnancy.

Briefly describe study procedures. Include any local site restrictions, for example, "Subjects enrolled at McLean will not participate in the pharmacokinetic portion of the study." Describe study endpoints.

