- 8.2.1.d. Availability and Flow of Subjects into Treatment. We plan to screen 50 subjects in the course of 20 months to achieve our desired sample size.
- 8.2.1.e. Study Visits. Following eligibility for the study (as determined by the baseline-1 visit), subjects will come to the laboratory for a baseline-2 visit to complete research assessments, provide a urine sample, and begin daily diaries and Actiwatch (see Section 8.5.2.a.) Subjects will then come to the clinic twice a week during the study medication treatment phase. One visit will include a medical visit (dispensing of pills and Medical Management; see Sections 8.3.1.b, 8.3.2) and research assessments, including a urine screen (see Section 8.5.2.a and Table 8.2). The other visit will consist only of a urine screen (see Section 8.5.2.a). After the 10-week treatment period, participants will have a follow-up assessment visit at 14 weeks. Subjects will also come in once weekly during weeks 11, 12, and 13 following the 10-week treatment period to provide a urine sample, and hand in daily diaries/actiwatch.

Subjects will be randomized to receive either dronabinol and clonidine or placebo. [name] or the research assistants will present 7 day prescriptions to the McLean pharmacy and the subject will receive blister packs containing 1 week of medication or placebo, separated into daily doses. Subjects will be asked to return unused pills at each weekly medical visit; study staff will then perform a pill count for the study record. All groups will receive capsules following the same schedule: 2 capsules three times daily for 10 weeks. Each capsule will contain either dronabinol, clonidine, or placebo. Subjects in the dronabinol-clonidine group will take 5 mg of dronabinol three times daily for 10 weeks (between 7:00-9:00 AM, 3:00-5:00 PM and 9:00-11:00 PM). Subjects in this group will also take clonidine 0.1 mg po bid (between 7:00-9:00 AM and 9:00-11:00 PM) for 8 weeks, followed by a taper to clonidine 0.1 mg po qhs for the last 2 weeks of

Partners Human Subjects Research Application Form

Version Date: July 26, 2016

the protocol. Subjects will be assessed for side effects prior to each dosing increase and the study physician will decide if increasing the dose as scheduled is appropriate. See Table 1 for a schedule of study visits.

Table 1	Cabadula	of Magazinas
i abie i	Scheaule	of Measures

Table 1 Schedule of Measures					
Measure	Baseline 1 and 2	•	_		Week 14

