Subjects who experience uncomfortable side effects (e.g., drowsiness or vertigo) may have their dose lowered from 2 capsules three times a day to 2 capsules twice daily by eliminating the middle dose of the day; a subject receiving active medication, for example, could then have a dronabinol dose reduction to 10 mg of dronabinol daily. If this leads to fewer side effects, the study physician will ask if the subject is willing to try the full dose again. If not, or if the subject tries the full dose again and is unable to tolerate it, the subject will be maintained on the lower dose. If a subject cannot tolerate 2 capsules twice per day, the medication will be discontinued, and the subject will be tapered off of the Clonidine, but the subject will continue to be followed for research visits. Similarly, we will monitor for potential cardiovascular side effects resulting from clonidine pharmacotherapy. At each medical management visit, we will assess vital signs and ask the subject about symptoms of orthostatic hypotension, such as dizziness when rising to stand from a seated position, blurry vision, or weakness. If subjects describe these symptoms without meeting exclusionary blood pressure criteria, we will hold the third set of capsules to see if this leads to fewer side effects, the study physician will ask if the subject is willing to try the full dose again. If not, or if the subject tries the full dose again and is unable to tolerate

Partners Human Subjects Research Application Form

Version Date: July 26, 2016

it, the subject will be maintained on the lower dose. If a subject cannot tolerate 2 capsules twice per day, the medication will be discontinued, but the subject will continue to be followed for research visits.

8.3.2. Medical Management Visits.

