All data collected will be de-identified with subject ID numbers and used for research purposes only. Written records will be kept in a locked file cabinet in a locked office. They will be destroyed after 5 years. Computerized data files will also be de-identified with subject ID numbers and kept in a password protected file on a password protected computer.

8.9. Statistical Analysis

The primary data analysis will be an intent-to-treat analysis, which includes all randomized subjects. Of note, every attempt will be made to continue assessing subjects even if they drop out of treatment. In addition, we will replicate all analyses with the completers only. The primary and secondary outcome variables are intended to

Partners Human Subjects Research Application Form Version Date: July 26, 2016

explore various aspects of response to therapy and to help define a clinically meaningful response. The primary outcome measures, Actiwatch-scores, daily diaries, TLFB self-report data, in addition to quantitative urinary THC metabolites, have been chosen for their ability to indicate daily use of cannabis by relying on self-report of use.

Specifically, for assessing the effect of dronabinol and clonidine on cannabis use patterns, we propose to use the generalized estimating equations (GEE) approach to longitudinal analysis, appropriately accounting for the positive correlation among repeated urine screen assessments within the same individual.

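### Section 8.2 sets a target of 18 completers at 8 per group: two groups of 8 make 16, and 18 completers does not fit the same paragraph's forecasts.

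*Combined protocol and SAP*

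**What the plan says.** Section 8.2 Participants (combined protocol and SAP) gives several counts in one paragraph:

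- The total: "A total of 18 cannabis-dependent volunteers with (9 men, 9 women) an Axis 1 psychiatric Disorder will serve as subjects".
- An attrition assumption: "Factoring in a potential 20% dropout of those who actually begin the protocol". The same sentence goes on to estimate that 7-8 people will be exposed to dronabinol.
- The target and group size: "In order to meet the target sample of 18 completers (8 subjects per group), we expect to recruit about 50 subjects". The sentence adds that 35 are expected to sign consent.
- The expected number entering the trial: "Of those who sign the informed consent form, 14-18 will probably end up being randomized".

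Section 8.1 Overview describes 18 subjects in a randomised trial, "with half receiving treatment with the combination of dronabinol and clonidine and half receiving placebo". Section 9.1 Sample Size gives a target sample of 18 without saying whether it counts people randomised or people completing. Section 8.9 Statistical Analysis makes the primary analysis intent-to-treat on everyone randomised, and adds a repeat of all analyses in completers only.

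**The concern.** The sentence that sets the recruitment target gives a total and a group size that cannot both hold with two equal arms. It also attaches the number 18 to completers, whereas section 8.1 and the first sentence of the paragraph attach it to all subjects. A reader cannot tell whether recruitment ends at 18 randomised, 18 completed or 16 completed.

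What is at stake is modest: the sample size that will be reported as planned, and how large the completers-only replication in section 8.9 was expected to be.

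**Working it through.** **Inputs.** Two arms at 1:1 (8.1). Target of 18 completers with 8 per group, total of 18 subjects, 14-18 randomised, 20% dropout, and 7-8 exposed to dronabinol (all 8.2). The documents give no alpha, power or effect size, and none is needed here.

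**Step 1: reproduce the plan's figure.** Total = arms x number per arm.
- 2 x 8 = 16, not 18.
- 18 / 2 = 9, not 8.

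The figure is not reproduced. This is a count within one sentence, so rounding or choice of formula cannot account for the difference of 2.

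**Step 2: look for a reading that gives both numbers.**

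| Reading | Arithmetic | Result |
|---|---|---|
| 8 per group are the completers from 18 randomised at 20% dropout | 18 x 0.8 / 2 | 7.2 per group |
| 16 completers from 18 randomised | 1 - 16/18 | 11% dropout, not 20% |
| 8 per group are randomised | 2 x 8 = 16; 16 x 0.8 | 12.8 completers |
| 16 completers after 20% loss | 16 / 0.8 | 20 randomised |
| 18 completers after 20% loss | 18 / 0.8 = 22.5 | 23 randomised; for equal arms 9 / 0.8 = 11.25, so 12 per arm, 24 |

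None gives 18 completers together with 8 per group. The last two need more than the 14-18 expected to be randomised.

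**Step 3: 18 completers against the number randomised.** Completers cannot exceed those randomised. With at most 18 randomised, 18 completers needs the very top of the range and no loss afterwards. If the 20% applies after randomisation, independently between subjects (an assumption), the chance that all 18 complete is 0.8^18 = 0.018, and the chance that at least 16 complete is 0.27.

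**Step 4: 18 completers against the exposure forecast.** At 1:1, 18 completers means 18 / 2 = 9 completing on active treatment, so at least 9 exposed to dronabinol. The plan expects 7-8. This conflict does not depend on where the 20% is applied. A target of 8 per group fits only the upper end of 7-8, and then only if every exposed person completes.

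**Step 5: what the paragraph supports.** With 18 randomised (9 per group) and 20% dropout, expected completers are 18 x 0.8 = 14.4, or 7.2 per group. The 7.2 is close to the plan's 7-8, which suggests that the 20% was taken from 18.

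**The case against.** The best defence is that this is a slip in a Stage 1 pilot feasibility study with no power calculation. No test, estimate or allocation depends on the parenthesis, and the primary analysis includes everyone randomised. That stands and limits the weight of the point, but it does not make the sentence right, and no other section repairs it.

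Several stronger readings are tempting, and the documents do not support them:

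- **That every other mention of 18 means total subjects.** Section 8.1 and the opening of the 8.2 paragraph do. Section 9.1 is silent on the matter, and omitting the word completers is not evidence of a different meaning.
- **That the plan will yield only 11-14 completers.** The figure 14 x 0.8 = 11.2 requires the 20% to be lost after randomisation from the lowest forecast. Because 18 x 0.8 = 14.4 lies near the bottom of 14-18, that range may already reflect the 20%, and 11.2 would then count dropout twice. On the other hand, 14-18 randomised at 1:1 puts 7-9 on active treatment, which is not quite the 7-8 stated. The documents do not settle which was meant.
- **That 18-23 people would have to begin.** If 14-18 is net of dropout, 14 / 0.8 = 17.5 is about the 18 already stated. The upper figure (18 / 0.8 = 22.5) arises only if 18 is also treated as net of loss.

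The plan also does not say whether a completer is someone who finishes treatment or someone who finishes assessments. That is a separate omission, and the arithmetic fails on either definition.

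**Conclusion.** The target is wrong as written. The core error is exact and rests only on two arms at 1:1: 16 against 18 in total, or 8 against 9 per group. The completer label conflicts with section 8.1, with the first sentence of the paragraph and, whatever the timing of dropout, with the 7-8 exposed to dronabinol. Its conflict with the 20% is firm if dropout follows randomisation; otherwise 18 completers is possible only when exactly 18 are randomised and none is lost later.

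The likeliest intent is 18 randomised, with about 14 completing (14.4) if the full 18 enter and 20% are lost; this is an inference and the sponsor should confirm it. The effect is confined to the stated sample size and the expected size of the completers-only replication. A reader might infer that the trial is short of its required size or that the main analysis is compromised. Neither follows: no required size was derived, and the primary analysis does not use the completer count.

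**What to change.** In section 8.2, replace the completer target and its parenthesis with wording such as: *a target of 18 randomised (9 per group); with 20% dropout about 14 expected completers (14.4, about 7 per group), fewer if fewer than 18 are randomised*.

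Then:

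1. Say at which point the 20% applies (before or after randomisation), and reconcile the 14-18 randomised and the 7-8 exposed with that statement. If the 20% is lost before randomisation, the expected completer count in the wording above must be restated.
2. Use the same label for 18 in sections 8.1, 8.2 and 9.1.

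If a completer target is really intended, keep one figure with its matching group size (16 with 8, or 18 with 9). State that 14-18 randomised does not deliver it if the 20% is lost after randomisation: 16 would need 20 randomised, and 18 would need 23, or 24 for equal arms.

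Cost: wording only, with no added patients, if 18 is the number randomised. Meeting a completer target under post-randomisation dropout would mean randomising 2 more than 18 (for 16 completers) or 5-6 more (for 18).

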8.2.1. Study Procedure

8.2.1.a. Recruitment and Intake.

Interested individuals will respond to advertisements by leaving a message (first name and call back number only) in the BPRL recruiting voice mailbox. Research

Partners Human Subjects Research

Application Form

assistants will call them back with 24 to 48 hours and conduct an initial phone screen that takes about 15 minutes. It will cover basic inclusion and exclusion criteria, as well as a brief description of the study to determine if the person is interested in participating. If the volunteer is appropriate and agrees to participate, they will be invited to come to the BPRL for a physical and psychiatric evaluation (SCID). Treatment alternatives will also be offered to the prospective participant if they decide not to participate or are not eligible for participation. We may also send letters to individuals from the "Gene regulation and linkage analysis in bipolar disorder and schizophrenia" study (protocol number: 2004p002535) who have previously consented to being contacted by letter.

Psychiatric Evaluation. A Structured Clinical Interview- DSM-IV (SCID) will be performed by a qualified research assistant, clinical psychologist, or psychiatrist.

Physical Exam. The medical exam will be performed by a physician. A blood draw and 12-lead ECG will be performed by a research assistant; results will be interpreted by a study physician.

Safety Monitoring. The subjects will undergo the following screening procedures: a) Detailed history of cannabis use; b) Review of DSM-IV criteria for cannabis dependence; c) Review of DSM-IV criteria for schizophrenia and schizoaffective disorder; d) Medical history and concomitant medication record; e) Physical examination; f) Laboratory screen that includes CBC, electrolytes, and BUN/creatinine; g) Urine measurement of THC; h) Urinalysis and urine pregnancy test for women; i) 12lead electrocardiograph (ECG); j) urine toxicology screen; k) blood alcohol testing; l) Positive and Negative Syndrome Scale (PANSS); m) Columbia Suicide Severity Rating Scale (C-SSRS). The study physician will perform a physical examination and obtain an ECG at baseline and at 14 weeks. Laboratory data (urinalysis, blood chemistries, complete blood count, electrolytes, and liver function tests) will be done at baseline, 5, 10, and 14 weeks as well. Given that according to its labeling, dronabinol should not be taken with alcohol, sedatives, hypnotics, or other psychoactive substances because they could potentiate the central nervous system effects of dronabinol, urine toxicology and blood alcohol testing will be done weekly along with the twice weekly quantitative THC urine screens during treatment. Women of childbearing potential will have urine pregnancy tests weekly each time a urine sample is given in addition to pregnancy tests at 4 and 8 weeks during treatment; women who become pregnant will have their medication discontinued and will be referred to an obstetrician; like all subjects, they will still be followed for research visits. Suicide risk will be assessed by the physician at each MM visit.

Study Restrictions

Subjects will be instructed to keep us informed of any medications initiated after their enrollment in the study. Subjects will be reminded of the potential for additive CNS depression resulting from concomitant use of dronabinol and alcohol, opioid analgesics, benzodiazepines, and barbiturates. They will be warned initially of these potential additive effects during the informed consent process. Participants will be warned not to drive, operate machinery, or engage in any hazardous activity while receiving dronabinol. Subjects will also be informed that clonidine may cause drowsiness, dizziness, or lightheadedness associated with orthostatic hypotension. These effects may be worse if taken with alcohol or other medications that can cause drowsiness. Subjects will be warned not to abruptly stop taking clonidine.

Partners Human Subjects Research Application Form

Subjects will also be informed that data on the use of antipsychotic medications and dronabinol and/or clonidine is lacking. Due to the potential for sedation and possible hypotension in subjects taking these medications together, we will monitor carefully for these symptoms while educating subjects about these possible side effects.

- 8.2.1.b. Informed consent. Eligible subjects will complete standard consent documentation. Prior to the volunteer being asked any question about his/her health, the volunteer will be given a consent form to read. The research assistant will go over it in detail with the volunteer. After a physician investigator answers any questions the volunteer may have concerning the study, he/she will be asked to provide their informed consent to the licensed physician investigator. If enrolled in the study, consent to communicate with their other clinicians will be obtained. Clinicians will be notified of their patients' enrollment in the study, thus allowing them to carefully monitor for changes in mood while they are undergoing treatment to stop use of cannabis.
- 8.2.1.c. Randomization. Research staff will stratify subjects according to their self-reported frequency of cannabis use in the past 30 days: 1) daily use; and 2) non-daily use. The stratification procedure will guard against the possibility that one of the experimental conditions (i.e., dronabinol-clonidine or placebo) will be overrepresented by daily users, while non-daily users will predominantly be randomized into the other condition.
- 8.2.1.d. Availability and Flow of Subjects into Treatment. We plan to screen 50 subjects in the course of 20 months to achieve our desired sample size.
- 8.2.1.e. Study Visits. Following eligibility for the study (as determined by the baseline-1 visit), subjects will come to the laboratory for a baseline-2 visit to complete research assessments, provide a urine sample, and begin daily diaries and Actiwatch (see Section 8.5.2.a.) Subjects will then come to the clinic twice a week during the study medication treatment phase. One visit will include a medical visit (dispensing of pills and Medical Management; see Sections 8.3.1.b, 8.3.2) and research assessments, including a urine screen (see Section 8.5.2.a and Table 8.2). The other visit will consist only of a urine screen (see Section 8.5.2.a). After the 10-week treatment period, participants will have a follow-up assessment visit at 14 weeks. Subjects will also come in once weekly during weeks 11, 12, and 13 following the 10-week treatment period to provide a urine sample, and hand in daily diaries/actiwatch.

Subjects will be randomized to receive either dronabinol and clonidine or placebo. [name] or the research assistants will present 7 day prescriptions to the McLean pharmacy and the subject will receive blister packs containing 1 week of medication or placebo, separated into daily doses. Subjects will be asked to return unused pills at each weekly medical visit; study staff will then perform a pill count for the study record. All groups will receive capsules following the same schedule: 2 capsules three times daily for 10 weeks. Each capsule will contain either dronabinol, clonidine, or placebo. Subjects in the dronabinol-clonidine group will take 5 mg of dronabinol three times daily for 10 weeks (between 7:00-9:00 AM, 3:00-5:00 PM and 9:00-11:00 PM). Subjects in this group will also take clonidine 0.1 mg po bid (between 7:00-9:00 AM and 9:00-11:00 PM) for 8 weeks, followed by a taper to clonidine 0.1 mg po qhs for the last 2 weeks of

Partners Human Subjects Research Application Form

Version Date: July 26, 2016

the protocol. Subjects will be assessed for side effects prior to each dosing increase and the study physician will decide if increasing the dose as scheduled is appropriate. See Table 1 for a schedule of study visits.

Table 1	Cabadula	of Magazinas
i abie i	Scheaule	of Measures

Table 1 Schedule of Measures					
Measure	Baseline 1 and 2	•	_		Week 14
		Week	1	Weeks 5,10	
Diagnostic Assessment					
Structured Clinical Interview	X B1				
for DSM-IV ^a	ABI				
Drug and Alcohol Assessment					
2. Quantitative Urine Toxicological	XB1,B2	X^{b}	X	X	X
Analysis ^b	•				
3. Addiction Severity Index	XB2		X	X	X
4. Drug and Alcohol Use Questionnaire	XB1				
5. Weekly Drug and Alcohol Use Inventory	XB1,B2	X	X	X	X
6. Marijuana Goals Questionnaire	XB1				
7. Marijuana Craving Questionnaire	XB1,B2	X	X	X	X
8. Marijuana Withdrawal Checklist	XB1,B2	X	X	X	X
Mood and Impulsivity Assessment					
9. Quick Inventory of Depressive	TID1 DA			***	***
Symptomatology	XB1,B2			X	X
10. Barratt Impulsiveness Scale	XB1,B2			X	X
11. Beck Anxiety Inventory	XB1,B2			X	X
Medical & Safety Assessment	VD1				37
12. Physical examination 13. ECG	XB1 XB1				X
	XB1,B2	X	X	X	X X
14. Urine pregnancy test	AD1,D2	Λ	Λ	Λ	Λ
15. Vital Signs ^c	XB1,B2	X	X	X	X
16. Positive and Negative Syndrome Scale	XB1,B2				
17. Behavioral Activity Rating Scale	XB1		X		
18. Laboratory tests ^d	XB1			X	X
19. Adverse Events & Side Effects	XB1,B2	X	X	X	X
20. Columbia Suicide Severity	XB1	X	X	X	X
21. Marijuana Perceptions of Risk and	XB1			X	X
Experiences Questionnaire (MPRE)					
Rating Scale					

^aFull SCID at baseline

8.2.1.f. Clinical Emergencies. If a subject is intoxicated, the subject will be evaluated medically, sent home in a taxi when safe, and the appointment re-scheduled. If a subject experiences a problem that requires clinical intervention during the course of the study (e.g., mania, suicidal ideation, or dangerous intoxication), we will evaluate the situation medically, make an appropriate recommendation, and help the subject to implement this plan. This could involve hospitalization at McLean, referral to the hospital's outpatient program, or other medical or psychiatric treatment, as clinically appropriate.

Partners Human Subjects Research Application Form

^bTwice a week during treatment

^cVital Signs include pulse and blood pressure (sitting and standing)

^dTests include urinalysis, liver function tests, electrolytes, complete blood count, & blood chemistries B1= Baseline 1 (screening visit)

B2=Baseline 2 (baseline 2 visit post screen for subjects who qualify for participation before treatment begins)

8.2.1.g. Subject Payments. Volunteers will receive a \$50 honorarium for attending the initial assessment interview, \$25 for baseline-2 visit, and \$50 for follow-up visits at 5, 10, and 14 weeks. They may earn \$25 for each urine sample given on a non-MM day in the first 5 weeks of the treatment and \$30 for each urine sample given on a non-MM day during the last 5 weeks of treatment. They will be compensated \$50 for the Week 1 monitoring visit and \$30 for each of three actiwatch diary UA visits at wks 11,12, and 13. They may also receive a bonus of up to \$100 for successful completion of all diaries. They may earn a total of \$740 for their participation in the study. Medication will be free.

A payment request will be submitted for each part of the study they finish. The research assistants will arrange for payment to be sent via mail to the subjects.

8.3. Treatment. ([name] has been granted IND 108676 by the FDA to use this medication combination in this protocol.)

Dronabinol (Marinol[®], Solvay Pharmaceuticals, Marietta, GA) is an orally-active cannabinoid agonist that is approved by the FDA for the treatment of anorexia associated with weight loss in patients with AIDS and nausea and vomiting associated with cancer chemotherapy (Marinol[®] product information). Dronabinol will be titrated to 5 mg three times daily in the dronabinol-clonidine group. Doses of up to 90 mg of dronabinol daily have been well-tolerated in studies of its effects upon cannabis-dependent individuals (Levin and Kleber 2008, Haney et al. 2008, Haney et al. 2004, Budney et al. 2007).

Clonidine (Catapres[®], Boehringer Ingelheim Pharmaceuticals, Ridgefield, CT) is α_2 -adrenergic agonist that is approved by the FDA for the treatment of hypertension (Catapres[®] product information). Clonidine will be administered at 0.1 mg twice daily in the dronabinol-clonidine group prior to a 2-week taper to clonidine 0.1 mg po qhs.

Placebo will be vegetable capsules (Gallipot, Inc., St. Paul, MN) double encapsulated into 00 capsules.

Physicians are ACLS-trained and have access to a "crash cart" located in the laboratory. All study personnel are basic life support-trained and have practiced assisting a physician in the event of an emergency.

8.3.1.c. Dose Adjustment.

Subjects who experience uncomfortable side effects (e.g., drowsiness or vertigo) may have their dose lowered from 2 capsules three times a day to 2 capsules twice daily by eliminating the middle dose of the day; a subject receiving active medication, for example, could then have a dronabinol dose reduction to 10 mg of dronabinol daily. If this leads to fewer side effects, the study physician will ask if the subject is willing to try the full dose again. If not, or if the subject tries the full dose again and is unable to tolerate it, the subject will be maintained on the lower dose. If a subject cannot tolerate 2 capsules twice per day, the medication will be discontinued, and the subject will be tapered off of the Clonidine, but the subject will continue to be followed for research visits. Similarly, we will monitor for potential cardiovascular side effects resulting from clonidine pharmacotherapy. At each medical management visit, we will assess vital signs and ask the subject about symptoms of orthostatic hypotension, such as dizziness when rising to stand from a seated position, blurry vision, or weakness. If subjects describe these symptoms without meeting exclusionary blood pressure criteria, we will hold the third set of capsules to see if this leads to fewer side effects, the study physician will ask if the subject is willing to try the full dose again. If not, or if the subject tries the full dose again and is unable to tolerate

Partners Human Subjects Research Application Form

Version Date: July 26, 2016

it, the subject will be maintained on the lower dose. If a subject cannot tolerate 2 capsules twice per day, the medication will be discontinued, but the subject will continue to be followed for research visits.

8.3.2. Medical Management Visits.

8.3.2.a. Weekly Visits with the Study Physician. Subjects will be seen weekly during treatment by the study physician for medical visits. In addition to dispensing the study medication, the physician will utilize Medical Management (MM) (Pettinati et al 2004), a manualized treatment that was used in the NIAAA COMBINE Study. MM was derived from empirically-tested manualized therapies (Carroll and O'Malley 1996, Mason and Goodman 1997) that were originally designed to approximate a primary care approach to the treatment of alcohol dependence. The treatment is delivered by a medical professional who monitors medication side effects, provides strategies to increase medication adherence (Volpicelli et al. 1997), and supports abstinence. The initial 40-60 minute session includes reviewing the cannabis dependence diagnosis and negative consequences from smoking marijuana, recommending abstinence, medication information, and offering strategies to enhance medication adherence. In subsequent 15-25 minute visits, recent substance use, overall functioning, medication adherence, and side effects are discussed. Session structure varies according to drug use status and medication adherence. If a subject is not adherent to the medication regimen, the clinician evaluates the reasons and helps the subject devise plans to enhance medication adherence. Subjects who use cannabis are given common-sense behavioral recommendations, such as avoiding parties where marijuana will be present. Presence and severity of side effects will be obtained through a standard. Adverse Events Checklist as well as the "Frequency and Intensity of Side Effects Rating/Global Report of Side Effects Burden" (Wisniewski et al. 1997), a 2-minute questionnaire that assesses the frequency, intensity, and level of burden of side effects. Medication adherence will be assessed in several ways, as outlined below in Section 8.6. These sessions will be audiotaped and a sample will be rated by a senior clinician in order to ensure fidelity to the MM process.

8.5. Research Measures.

See Table 8.2 for the schedule of assessments.

8.5.1. Diagnostic Assessment. To make the diagnoses of cannabis dependence, the Structured Clinical Interview for DSM-IV (SCID) (First 1996) will be used.

8.5.2. Drug and Alcohol Use Assessment.

8.5.2.a. Urine Screens. The primary outcome measure will be cannabis use, as measured by twice-weekly quantitative urine screens during treatment. Quantative urine screens will also be measured during weeks 11, 12, 13, and 14 following the 10-week treatment period. Cannabis is a particularly challenging drug of abuse for measuring outcome because of the false-positive urine screens that can occur as the result of long-term accumulation of cannabis metabolites. In an attempt to avoid false-positive results, we will obtain 2 supervised urine samples weekly: 1 at the medical visit and 1 on another day, ordinarily with 3-4 days separation from the clinical visits (e.g., Monday-Thursday, Tuesday-Friday, or Monday-Friday); this should maximize the time frame covered by our urine screens. We will send the urine samples to Quest Diagnostics Laboratory (Cambridge, MA, a NIDA-certified laboratory), where the urines

Partners Human Subjects Research Application Form Version Date: July 26, 2016

will be screened by immunoassay for the THC metabolite 11-nor-carboxy-∆ 9tetrahydrocannabinol (THC-COOH) as well as other drugs of abuse. Urine creatinine concentrations will also be measured to assess urine concentration. The threshold for detection of THC-COOH will be 20 ng/ml. Samples positive for this metabolite will undergo further analysis by gas chromatography-mass spectroscopy to obtain quantitative THC-COOH concentration; we will then calculate the ratio of this metabolite to urine creatinine concentration. We will adopt the method of Heustis and Cone (1998) to differentiate new marijuana use from residual drug excretion as a result of previous use; these recommendations are based on their controlled clinical studies of urinary excretion profiles of creatinine and marijuana metabolites following marijuana administration in humans. We will label a urine negative (i.e., abstinent from cannabis) if 1) the ratio of THC-COOH to creatinine in the urine does not increase by >50% from the ratio obtained in the previous urine screen, and 2) the subject also reports using no cannabis since the previous urine test.

8.5.2.b. Self-Report. We will use 3 methods of self-report in an effort to determine the most appropriate and effective method for use in this population. An ActiWatch-Score will be determined via compact, wrist-worn, battery-operated activity monitors that are excellent devices for monitoring multiple drug use, drug craving, and sleep/wake activity (Licata et al., under review). We will provide subjects with a packet of 1 page, selfaddressed, prepaid postage Daily Diary pages which subjects will be asked to fill out between 7:00 and 9:00 a.m. each day and hand them in during their weekly visits. The diary consists of a series of questions about marijuana and other drug use as well as eating habits. During weeks 11, 12, and 13 subjects will have 1 weekly Diary/Actiwatch visit to hand in their daily diaries, , provide a urine sample, and have their Actiwatch data downloaded. During the weekly visits, we plan to collect cannabis use data using the Timeline Follow Back (TLFB) (Sobel and Sobel 1992) protocol that was developed for alcohol.

